### 5.1.1 Toxicity Management

Participants whose treatment is interrupted or permanently discontinued due to an adverse event or abnormal laboratory value suspected to be related to idelalisib will be followed until the adverse event or abnormal laboratory resolves or returns to grade 1. If a participant requires a dose delay of 28 days or longer, then the participant must be discontinued from the study. All interruptions or changes to study drug administration must be recorded.

It will be documented whether or not each participant completed the clinical study. The reason either study treatment or observations were discontinued will be recorded. Reasons that a participant may discontinue participation in a clinical study are considered to constitute one of the following:

1. Adverse event(s)
2. Abnormal laboratory value(s)
3. Abnormal test procedure result(s)
4. Disease progression (including initiation of new therapy)
5. Protocol violation
6. Participant withdrew consent
7. Lost to follow-up
8. Administrative problems (including study-related issues, IRB and other regulatory issues, and drug administration issues)
9. Death
10. General or specific changes in the participant's condition that render the participant unacceptable for further treatment in the opinion of the treating investigator.

Participants who meet any criteria 1-4 above but are deemed by the investigator to be clinically benefiting from idelalisib (i.e. remain asymptomatic or IgM levels not increasing further) will be permitted to continue on protocol at the Principal Investigator's discretion. Clinical benefit is determined by considering clinical data, such as overall participant performance and disposition, CBC, and when necessary, bone marrow biopsy results and CT scans.

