#### 4.1.3 Duration of Therapy

Duration of therapy will depend on individual response, evidence of disease progression and tolerance. In the absence of treatment delays due to adverse events, treatment may continue until one of the following criteria applies:

- Disease progression (including initiation of new therapy) or death
- Dose delay of >28 days for toxicity
- Intercurrent illness that prevents further administration of treatment
- Unacceptable toxicity or adverse event(s)
- Participant demonstrates an inability or unwillingness to comply with the oral medication regimen and/or documentation requirements
- Participant decides to withdraw from the study
- General or specific changes in the participant's condition render the participant unacceptable for further treatment in the opinion of the treating investigator.

**Participants who meet criteria for disease progression but are deemed by the investigator to be clinically benefiting from idelalisib will be permitted to continue on protocol at the Principal Investigator's discretion. Clinical benefit is determined by considering clinical data, such as overall participant performance and disposition, CBC, and when necessary, bone marrow biopsy results and CT scans.**

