#### 4.1.4 Duration of Participation

Participants will continue to take Idelalisib per-protocol until disease progression or unacceptable adverse event. Study visits will occur two weeks after starting Idelalisib, then monthly from the start of Idelalisib for three months, followed by every three months from the start of Idelalisib thereafter until disease progression or the start of another line of therapy, whichever occurs first. For patients who have responded but come off Idelalisib for reasons other than progression, they will be followed every 6 months until progression or another line of therapy. An end of study visit will take place 30 days following the last dose of Idelalisib. The duration for individuals, and duration of the study, are dependent upon disease response. We anticipate no more than 2 years duration for individual subjects. We anticipate the study will remain active for a total of 4 years including enrollment, treatment, follow-up and data analysis.

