Neutropenia	ANC 1.0 to <1.5 Gi/L	ANC 0.5 to <1.0 Gi/L	ANC <0.5 Gi/L
	Maintain Idelalisib dose.	Maintain Idelalisib dose. Monitor ANC at least weekly.	Interrupt Idelalisib. Monitor ANC at least weekly until ANC $\geq$ 0.5 Gi/L, then may resume Idelalisib at 100 mg BID (or if taking 150mg BID, decrease to 100mg).
Thrombocytopenia	Platelets 50 to <75 Gi/L	Platelets 25 to <50 Gi/L	Platelets <25 Gi/L
	Maintain Idelalisib dose.	Maintain Idelalisib dose. Monitor platelet counts at least weekly.	Interrupt Idelalisib. Monitor platelet count at least weekly. May resume Idelalisib at 100 mg BID (or if taking 150mg BID, decrease to 100mg) when platelets $\geq$ 25 Gi/L.

Abbreviations: ALT, alanine aminotransferase; AST, aspartate aminotransferase; ANC, absolute neutrophil count; BID, twice daily; ULN, upper limit of normal

Dose re-escalations will not be permitted once dose reduced to next lower dose level. If a participant requires a dose delay of 28 days or more, then the participant must be discontinued from the study.

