For women of childbearing potential only: Serum pregnancy test is required at screening.If bone marrow biopsy and aspiration must have been repeated following any previous therapy > 1 cycle.These visits including physical exam and blood work may be performed by local physician and confirmed by telephone contact if patient unable to return for week 2 visit or monthly visits on months 1 and 2.CBC with differential should be monitored every 2 weeks for the first 6 months of treatmentHepatic function tests should be checked every 2 weeks for the first 3 months of treatmentWhile on study drug or until disease progression or start of another therapy.30 days following last dose (+/-) 7 days.

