#### 8.5 Progression-Free Survival

Progression-Free Survival (PFS) is defined as the duration of time from start of treatment to time of objective disease progression (including initiation of new therapy or death). Follow-up will continue until disease progression, which we anticipate to be no more than 2 years.

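### The 28-day dose-delay rule in Sections 5 and 5.1.1 takes participants off the study, not just off drug, and as worded conflicts with the disease follow-up in 4.1.4 and 8.5

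*Combined protocol and SAP*

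**What the plan says.** Four parts of the protocol bear on what happens after a long dose delay.

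- **Removal from the study.** Section 5.1.1: "If a participant requires a dose delay of 28 days or longer, then the participant must be discontinued from the study". Section 5, below the dose-modification table: "If a participant requires a dose delay of 28 days or more, then the participant must be discontinued from the study".
- **End of treatment only.** Section 4.1.3 lists criteria for stopping treatment. One of them is "Dose delay of >28 days for toxicity".
- **Disease follow-up.** Section 4.1.4: "For patients who have responded but come off Idelalisib for reasons other than progression, they will be followed every 6 months until progression". Starting a different treatment also ends this follow-up. The same section sets quarterly visits, counted from drug start, that run to progression or a new line of treatment. Section 8.5 adds: "Follow-up will continue until disease progression, which we anticipate to be no more than 2 years". Calendar footnote 6, on the three-monthly column, reads: "While on study drug or until disease progression or start of another therapy".
- **The visit after the last dose.** Section 4.1.4: "An end of study visit will take place 30 days following the last dose of Idelalisib". The calendar labels it the End of Study Treatment Visit and times it at "30 days following last dose (+/-) 7 days". It is marked for examination, performance status, adverse events, blood count, chemistry and liver tests. It is blank for serum free light chains, SPEP/SIFE/immunoglobulins and UPEP/UIFE.

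**The concern.** A participant cannot be off the study and also be followed to progression. If a site obeys Sections 5 and 5.1.1 as written, disease follow-up ends at a 28-day delay. Section 5.1.1 keeps following the adverse event until it resolves or returns to grade 1, but says nothing there about disease status.

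PFS is a secondary endpoint, and under 8.5 its events are progression, new therapy and death. Stopping observation could lose all three. The reason for stopping would be toxicity, which may be related to prognosis, so the censoring could be informative. Observations that were never made cannot be recovered at analysis.

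A smaller point concerns the visit about 30 days after the last dose. On the literal reading it could be the last contact, yet none of the tests on which 8.2 bases hematologic progression (serum M-protein, urine M-protein, free light chains) is scheduled there.

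**Working it through.** The plan gives no figure for this point, so the check is a comparison of the texts followed by a rough scale.

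**1. Text comparison**

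| Place | Threshold | What ends |
|---|---|---|
| 4.1.3 | more than 28 days, for toxicity | treatment |
| 5 | 28 days or more | participation in the study |
| 5.1.1 | 28 days or more | participation in the study |
| 4.1.4, responders off drug without progression | none | nothing: visits every 6 months to progression or new therapy |
| 8.5 | none | nothing: follow-up to progression |

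Rows 2 and 3 conflict with row 1 on both threshold and consequence, and with rows 4 and 5 on follow-up. A delay of exactly 28 days triggers Sections 5 and 5.1.1 but not 4.1.3.

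**2. Whether the 28-day route can occur**

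After a liver hold, Section 5 allows drug to resume only when ALT/AST or bilirubin is below 1 x ULN. The exclusion criteria admit patients with ALT/AST up to 2.5 x ULN and bilirubin up to 1.5 x ULN. A patient who enrolled above 1 x ULN would have to improve on baseline before resuming. A hold of 28 days is therefore plausible, though the documents give no rate for it.

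**3. Upper scale**

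Assume that every adverse-event stop goes through the 28-day rule, using the rates in Section 2.1.6 and N = 18:

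- 101-02/101-99, 12%: 18 x 0.12 = 2.16
- 101-09, 19 of 125: 18 x 19/125 = 2.74
- 101-10, 2 of 11 (the 11 is inferred from 10 patients being 91%): 18 x 2/11 = 3.27

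The top of the range is about 3 of 18. The bottom is 0. Symptomatic pneumonitis, perforation, positive CMV PCR, ALT/AST or bilirubin above 10 x ULN and life-threatening diarrhea all stop drug directly. In addition, this trial starts at 100 mg BID, whereas 101-09 used 150 mg BID.

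**4. Dependence on the PFS definition**

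Section 8.5 counts PFS from the start of treatment, so all patients are exposed. Section 1.1.7 counts from first response, so only responders are. At the design response rate of 25% (Section 12.2) there are 18 x 0.25 = 4.5 responders. If response and toxicity exit are independent (an assumption), the affected responders number 2.74 x 0.25 = 0.68, or 3.27 x 0.25 = 0.82 on the largest rate, so fewer than one.

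**5. Test gap at the end visit**

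From month 3 the tests are about 91 days apart. Let the hold start s days after a quarterly visit. On the literal reading participation ends at s + 28, so the next quarterly test is lost only if s + 28 <= 91, that is s <= 63. The end visit falls at s + 30, so the longest gap is 63 + 30 = 93 days, or 100 with the 7-day window. Against the routine 91 days that is 2 days longer, or 9 with the window.

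**The case against.** The strongest reply is that study here means study treatment, and the text gives real support for it.

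- One visit carries two names: end of study in 4.1.4 and end of study treatment in the calendar.
- The 5.1.1 list of reasons for ending participation largely tracks the treatment-stopping list in 4.1.3.
- Section 5.1.1 lets patients who are benefiting continue on protocol, in a context where that means continuing on drug.
- Section 2.1.6 uses discontinued treatment and discontinued the study almost interchangeably.

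This stands as a plausible account of intent. It does not remove the conflict. Section 5.1.1 itself distinguishes stopping treatment from stopping observation, and Section 5 speaks of an off-study visit after which it mentions only toxicity contact.

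A reader might infer that non-responders have no follow-up once off drug. The documents do not support that. The quarterly visits in 4.1.4 are anchored to drug start and end at progression or new therapy, and footnote 6 is consistent with this. Moving these patients to 6-monthly visits could halve their assessment frequency.

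A reader might also take the 93-day gap as a serious hole. It barely exceeds the interval that every patient on drug already has from month 3, and it arises only on the literal reading.

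Finally, Section 12 specifies no hypothesis test on PFS, so no planned decision rests on it. That limits the weight of the point, but the wording still needs correcting.

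**Conclusion.** The conflict in wording is real and worth correcting, at modest priority. Followed literally, Sections 5 and 5.1.1 end PFS follow-up for a toxicity-related reason in 0 to about 3 of 18 patients under the 8.5 definition, and in fewer than one responder under the 1.1.7 definition. The upper end rests on borrowed discontinuation rates and on every adverse-event stop passing through the 28-day rule; the true number is likely lower.

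It would go too far to conclude that PFS will be biased. The size and direction of any bias cannot be derived from the documents, and there is none if the off-drug hazard is unchanged. Nor is the primary hematologic response conclusion at risk, because Section 12.4 keeps all eligible enrolled participants in that analysis. The blank tests at the end visit are a secondary gap that is easy to close.

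**What to change.** - **Sections 5 and 5.1.1:** for a delay of 28 days or more, write *idelalisib must be permanently discontinued; the participant remains on study for disease follow-up per 4.1.4 and 8.5 unless consent is withdrawn*.
- **Section 4.1.3:** change the threshold to *28 days or more*.
- **Off-drug schedules:** leave them as they are. Responders stay on 6-monthly visits. Non-responders keep the three-monthly visits of 4.1.4 and footnote 6 until progression or new therapy.
- **Calendar (a cheap addition):** mark serum free light chains, SPEP/SIFE/immunoglobulins and UPEP/UIFE at the End of Study Treatment Visit, so that it can establish hematologic progression under 8.2.

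The cost is wording in three sections and three calendar entries. Per participant it adds one urine sample and a few assays on blood that is already drawn at that visit. Dosing, sample size and the primary analysis do not change.

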### 5. EXPECTED TOXICITIES AND DOSING DELAYS/DOSE MODIFICATIONS

If possible, symptoms should be managed symptomatically. In the case of toxicity, appropriate medical treatment should be used (including anti-emetics, anti-diarrheals, etc.). All adverse events experienced by participants will be collected from the time of the first dose of study treatment, through the study and until the final study visit. Participants continuing to experience toxicity at the off study visit may be contacted for additional assessments until the toxicity has resolved or is deemed irreversible.

For patients who are unable to tolerate the protocol-specified dosing schedule, dose adjustments are permitted. If administration of idelalisib must be interrupted because of unacceptable toxicity, drug dosing will be interrupted or modified according to the manufacturer's guidelines seen below. Toxicities requiring dose modification that recur upon restarting drug should be discussed with the principal investigator.

Dose Modifications for Toxicities Due to Idelalisib			
Pneumonitis: Discontinue Idelalisib in patients with any severity of symptomatic pneumonitis			
Intestinal Perforation: Discontinue Idelalisib			
Positive CMV PCR: Consider confirmation (at investigator discretion) Discontinue Idelalisib			
ALT/AST	>3-5 x ULN	>5-10 x ULN	>10 x ULN
	Maintain Idelalisib dose. Monitor at least weekly until <1 x ULN.	Withhold Idelalisib. Monitor at least weekly until ALT/AST are <1 x ULN, then may resume Idelalisib at 100 mg BID (or if taking 150mg BID, decrease to 100mg).	Discontinue Idelalisib permanently.

Bilirubin	>1.5-3 x ULN	>3-10 x ULN	>10 x ULN
	Maintain Idelalisib dose. Monitor at least weekly until <1 x ULN.	Withhold Idelalisib. Monitor at least weekly until bilirubin is <1 x ULN, then may resume Idelalisib at 100 mg BID (or if taking 150mg BID, decrease to 100mg).	Discontinue Idelalisib permanently.
Diarrhea	Moderate diarrhea (increase of 4-6 stools/day over baseline)	Severe diarrhea or Hospitalization (increase of 7 or more stools/day over baseline)	Life-threatening diarrhea
	Maintain Idelalisib dose. Monitor at least weekly until resolved.	Withhold Idelalisib. Monitor at least weekly until resolved, then may resume Idelalisib at 100 mg BID (or if taking 150mg BID, decrease to 100mg).	Discontinue Idelalisib permanently.

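### Section 5.1.1 allows discretionary continuation after adverse events or abnormal results and exempts none of the six discontinuation instructions in section 5

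*Combined protocol and SAP*

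**What the plan says.** The dose-modification table in section 5 contains six instructions to stop the drug. For pneumonitis it reads "Discontinue Idelalisib in patients with any severity of symptomatic pneumonitis". Intestinal perforation is also a stop. For a positive CMV PCR it reads "Consider confirmation (at investigator discretion) Discontinue Idelalisib". The top grade of the ALT/AST, bilirubin and diarrhea rows each reads "Discontinue Idelalisib permanently".

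Section 5.1.1 lists ten reasons for leaving the study, introduced by "Reasons that a participant may discontinue participation in a clinical study are considered to constitute one of the following". The first four are adverse events, abnormal laboratory values, abnormal test procedure results and disease progression. It then makes an exception: "Participants who meet any criteria 1-4 above but are deemed by the investigator to be clinically benefiting from idelalisib", with benefit glossed as "remain asymptomatic or IgM levels not increasing further) will be permitted to continue on protocol", at the Principal Investigator's discretion. On how benefit is judged it says "Clinical benefit is determined by considering clinical data, such as overall participant performance and disposition, CBC", adding bone marrow biopsy and CT when needed.

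Section 4.1.3 has a near-identical clause with a narrower scope: "Participants who meet criteria for disease progression but are deemed by the investigator to be clinically benefiting from idelalisib will be permitted to continue". The same section lists unacceptable toxicity or adverse events as a reason to end treatment and attaches no exception to it.

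**The concern.** The section 5 table tells the investigator to stop. A later paragraph of the same section tells the investigator that a participant with an adverse event or abnormal result may carry on. Nothing says which governs when both apply.

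This is a matter of patient safety and trial conduct. The laboratory stops exist to act on results that may appear before symptoms do, yet one limb of the benefit test is the absence of symptoms. The protocol treats CMV as serious elsewhere. A positive CMV PCR excludes a patient at entry (3.2.13), it is tested monthly on treatment (section 7), and section 2.1.5 names CMV among the infections behind excess deaths in phase 3 add-on studies in other settings. A clause that could keep a CMV-positive participant on idelalisib works against those provisions. Two participants with the same result could also be handled differently, depending on how the text is read.

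**Working it through.** There is no figure in the plan to reproduce. The check is a comparison of text, with a count of rules.

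**Step 1. The stops, and whether 5.1.1 reaches them.**

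| Section 5 stop | Trigger | 5.1.1 criterion it can fall under | Exempted in 5.1.1? |
|---|---|---|---|
| Symptomatic pneumonitis | Clinical | 1 | No |
| Intestinal perforation | Clinical | 1 | No |
| Positive CMV PCR | Laboratory | 2 or 3 | No |
| ALT/AST >10 x ULN | Laboratory | 1 or 2 | No |
| Bilirubin >10 x ULN | Laboratory | 1 or 2 | No |
| Life-threatening diarrhea | Clinical | 1 | No |

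Stops: 3 clinical + 3 laboratory = 6. Exempted: 0 of 6. The neutropenia and thrombocytopenia rows call for interruption, so they are not counted.

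**Step 2. Scope of the two exceptions.** Section 5.1.1 covers four criteria, of which 4 - 1 = 3 are not progression. Section 4.1.3 covers one, progression.

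**Step 3. Does the benefit test act as a safeguard?** It is met by either limb: no symptoms, or IgM not rising further. On a literal reading, even a participant with symptomatic pneumonitis and stable IgM could qualify. The data named for judging benefit are performance, disposition, CBC, marrow and CT. They include 0 of the 3 laboratory stop values, although the list is given as examples and is not exhaustive.

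**Step 4. Do other sections settle it?**
- Section 10.2 says discontinuation follows section 5, but 5.1.1 is part of section 5.
- Section 4.1.4 provides six-monthly follow-up off drug, but only for responders.
- Benefit is described as coming from idelalisib, and the twin clause sits under Duration of Therapy. Both point to continued dosing.

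**Step 5. How often could such a result surface?** Section 7 schedules hepatic tests every 2 weeks for the first 3 months and CMV PCR monthly. Over about 13 weeks, 13/2 = 6.5, so about 6 hepatic panels. Adding 3 CMV PCRs gives about 9 scheduled tests per participant. These are opportunities to see a stop value, not events.

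**Step 6. The 28-day rule.** Section 4.1.3 ends treatment after a delay of more than 28 days; sections 5 and 5.1.1 do so at 28 days or longer. Stopping at 28 days satisfies all three, so the mismatch is editorial. A dose delay is not one of criteria 1-4, and 5.1.1 states its own delay rule as mandatory, so it is not counted among the six.

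**The case against.** The best reply is that the sections can be read together.

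- A specific table row would ordinarily prevail over a general clause.
- Staying on protocol could mean follow-up without drug. The 5.1.1 list concerns participation, and that section opens by following anyone whose treatment is stopped for an adverse event or abnormal laboratory value until it resolves or returns to grade 1. That follow-up is not limited to responders.
- The table is headed as covering toxicities due to idelalisib, whereas criteria 1-3 carry no attribution. The clause therefore has an ordinary use for unrelated events or those below a stop threshold.
- Sections 1.1.2, 4.1.4 and 12.0 all have treatment end at progression or unacceptable toxicity.

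There are also practical checks. Continuation needs the investigator's judgement of benefit and the Principal Investigator's discretion. Laboratory reports are reviewed at weekly program meetings, and the DSMC reviews the study at least annually. Section 2.1.5 also reports no increased risk of death in the relapsed CLL phase 3 studies.

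Much of this stands. It makes the literal override less likely, and a careful investigator may well apply the protective reading. But none of these readings is stated as the rule, and 5.1.1 names the same kinds of event that the table governs. Two smaller points are also fair. The test count measures the monitoring schedule, not harm. And the documents do not show that bilirubin >10 x ULN would be free of symptoms, so CMV PCR and ALT/AST are the clearer cases.

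**Conclusion.** The concern holds and should be fixed. The mismatch is certain on the text. Whether a participant would in practice be kept on drug past a stop depends on how the investigators read an ambiguous clause.

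The size can be given only as a count of rules: none of six stops is protected, and the exposure is greatest for the three triggered by a laboratory result. The number of participants affected cannot be calculated without an event rate in this population. The conclusion assumes that continuing on protocol includes continued dosing, which is the more natural reading but not the only one.

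**What to change.** Add one sentence to section 5.1.1: *This exception never overrides a Discontinue instruction in section 5 or the 28-day dose-delay rule.* Discretion remains for adverse events that have no stop rule. If the sponsor already intends the table to prevail, practice does not change.

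An alternative is to limit the exception to progression, as in 4.1.3. That would also remove discretion for adverse events without a stop rule, so it is a trade-off and is not required. As an editorial tidy-up, align the delay limit in 4.1.3 with the 28 days or more used in section 5.

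The cost is one sentence in an amendment and a small loss of discretion at the six stops. It needs no extra participants, visits or procedures and leaves alpha, power and sample size unchanged.
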